path\t_program.sas date time

Programmer note sort by visit date within each subject

Programmer note If No or Not Done is recorded on the CRF to indicate that vital signs were not collected, show "Not Done" under the Visit Date column.

Listing 34
Copies of VM202 in Whole Blood

Treatment Group	Subject ID	Visit	Pre/Post Injection	Visit Date (Study Day)	Was a Sample to Test VM202 Obtained? ^[1]	Time Obtained
Placebo	xxxxxx	visit visit	Pre/Post Pre/Post	date9. (xx) date9. (xx)	Yes/No Yes/No	Time5. Time5.
				...		
VM202- 8 mg	xxxxxx	visit visit	Pre/Post Pre/Post	date9. (xx) date9. (xx)	Yes/No Yes/No	Time5. Time5.
				...		
VM202- 16 mg	xxxxxx	visit visit	Pre/Post Pre/Post	date9. (xx) date9. (xx)	Yes/No Yes/No	Time5. Time5.
				...		

Note: Study Day = [(Date of Event) - (Treatment Start Date)]; 1 is added to the difference when 'Date of Event' is greater than or equal to 'Treatment Start Date'.

^[1] For Post Injection time points, result shown is to the question "Was a sample to test VM202 obtained (required between 1-3 hours post injection)?"

path\t_program.sas date time

Programmer note sort by visit date within each subject

Listing 35
Serum Hepatocyte Growth Factor (HGF)

Treatment Group	Subject ID	Visit	Visit Date (Study Day)	Was a Sample to Test Serum HGF Obtained?	Time Obtained
Placebo	xxxxxx	visit	date9. (xx)	Yes/No	Time5.
		visit	date9. (xx)	Yes/No	Time5.
			...		
VM202- 8 mg	xxxxxx	visit	date9. (xx)	Yes/No	Time5.
		visit	date9. (xx)	Yes/No	Time5.
			...		
VM202- 16 mg	xxxxxx	visit	date9. (xx)	Yes/No	Time5.
		visit	date9. (xx)	Yes/No	Time5.
			...		

Note: Study Day = [(Date of Event) - (Treatment Start Date)]; 1 is added to the difference when 'Date of Event' is greater than or equal to 'Treatment Start Date'.
path\t_program.sas date time

Programmer note sort by visit date within each subject

Listing 36
Eye Examination - Retinal Fundoscopy

Treatment Group	Subject ID	Visit	Examination Performed?	Date of Examination (Study Day)		Results		
				Retinal Fundoscopy	Fluorescein Angiography	OD (Right)	If Abnormal, describe:	OS(Left)
Placebo	xxxxxx	Visit	Yes/No	Date9. (xx)	Date9. (xx)	Result		Result
		Visit	Yes/No	Date9. (xx)	Date9. (xx)	Result#	xxxxxxxx	Result*
				...				xxxxxxxx
VM202- 8 mg	xxxxxx	Visit	Yes/No	Date9. (xx)	Date9. (xx)	Result		Result
		Visit	Yes/No	Date9. (xx)	Date9. (xx)	Result		Result
				...				
VM202- 16 mg	xxxxxx	Visit	Yes/No	Date9. (xx)	Date9. (xx)	Result		Result
		Visit	Yes/No	Date9. (xx)	Date9. (xx)	Result		Result
				...				

Note: Study Day = [(Date of Event) - (Treatment Start Date)]; 1 is added to the difference when 'Date of Event' is greater than or equal to 'Treatment Start Date'.

Note: # Abnormal – Not Clinically Significant. * Abnormal - Clinically Significant.

path\t_program.sas date time

Programmer note sort by date of exam within each subject (sort by variable OSDT1). Results presented as Normal or Abnormal.

Listing 37
Injection Site Reaction

Treatment Group	Subject ID	Visit	Pre/Post Injection	Visit Date (Study Day)	Was There an Injection Site Reaction? ^[1]	If YES, AE #
Placebo	xxxxxx	visit visit	Pre/Post Pre/Post	date9. (xx) date9. (xx)	Yes/No Yes/No	x x
			
VM202- 8 mg	xxxxxx	visit visit	Pre/Post Pre/Post	date9. (xx) date9. (xx)	Yes/No Yes/No	x x
			
VM202- 16 mg	xxxxxx	visit visit	Pre/Post Pre/Post	date9. (xx) date9. (xx)	Yes/No Yes/No	x x
			

Note: Study Day = [(Date of Event) - (Treatment Start Date)]; 1 is added to the difference when 'Date of Event' is greater than or equal to 'Treatment Start Date'.

^[1] For Pre Injection time Points, response shown is to the question "If an injection site reaction occurred at the previous visit, is it still present?"

path\t_program.sas date time

Programmer note sort by visit date within each subject

Listing 38
Prior and Concomitant Medications

Treatment Group	Subject ID	CM #	Medication// Drug Name	Start Date (Study Day)	Stop Date (Study Day)	Dose	Units	Route	Regimen	Indication
Placebo	xxxx	1	Medication/Drug Name	Date9.(xx)	Date9.(xx)	xxxx	unit	route	regimen	Medical History #/ Adverse Event #/ Other: specify
		2	Medication/Drug Name	Date9.(xx)	Ongoing	xxxx	unit	route	regimen	Medical History #/ Adverse Event #/ Other: specify
VM202- 8 mg	... xxxx	1	Medication/Drug Name	Date9.(xx)	Date9.(xx)	xxxx	unit	route	regimen	Medical History #/ Adverse Event #/ Other: specify
		2	Medication/Drug Name	Date9.(xx)	Ongoing	xxxx	unit	route	regimen	Medical History #/ Adverse Event #/ Other: specify
VM202- 16 mg	... xxxx	1	Medication/Drug Name	Date9.(xx)	Date9.(xx)	xxxx	unit	route	regimen	Medical History #/ Adverse Event #/ Other: specify
		2	Medication/Drug Name	Date9.(xx)	Date9.(xx)	xxxx	unit	route	regimen	Medical History #/ Adverse Event #/ Other: specify
...										

Note: Study Day = [(Date of Event) - (Treatment Start Date)]; 1 is added to the difference when 'Date of Event' is greater than or equal to 'Treatment Start Date'.
path\t_program.sas date time

Programmer Note sort by CM #.

Programmer Note If Ongoing is marked, then show "Ongoing" in the Stop Date column.

Listing 39
Prior and Concomitant Procedures

Treatment Group	Subject ID	Procedure #	Procedure Name	Date of Procedure (Study Day)	For Procedures Related to Peripheral Vascular Disease	
					Surgical Site	Leg
Placebo	xxxx	1	xxxx unit	date9. (xx)	description	left/right
		2	xxxx unit	date9. (xx)	description	left/right
VM202- 8 mg	xxxx	1	xxxx unit	date9. (xx)	description	left/right
		2	xxxx unit	date9. (xx)	description	left/right
VM202- 16 mg	xxxx	1	xxxx unit	date9. (xx)	description	left/right
		2	xxxx unit	date9. (xx)	description	left/right
...						

Note: Study Day = [(Date of Event) - (Treatment Start Date)]; 1 is added to the difference when 'Date of Event' is greater than or equal to 'Treatment Start Date'.
path\t_program.sas date time

Programmer note sort by date of procedure within each subject

Listing 40
Death Report

Treatment Group	Subject ID	Date of Death (Study Day)	Cause of Death	Comments
Placebo	xxxx	Date9. (Study Day)	Description	Yes/No
	xxxx	Date9. (Study Day)	Description	Yes/No
	...			
VM202- 8 mg	xxxx	Date9. (Study Day)	Description	Yes/No
	xxxx	Date9. (Study Day)	Description	Yes/No
	...			
VM202- 16 mg	xxxx	Date9. (Study Day)	Description	Yes/No
	xxxx	Date9. (Study Day)	Description	Yes/No
	...			

Note: Study Day = [(Date of Event) - (Treatment Start Date)]; 1 is added to the difference when 'Date of Event' is greater than or equal to 'Treatment Start Date'.
path\t_program.sas date time

Programmer note cause of death description includes AE#, for SAE, and specification for Other.

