1.6. PRECLINICAL DATA

The non-clinical safety of VM202 has been evaluated for general toxicity following single intramuscular and intravenous doses in rats. In addition, the general toxicity of VM202 following multiple intermittent (weekly or monthly) intramuscular doses has been evaluated in rabbits and rats, respectively. The potential for genomic integration at the injection site as well as the potential for distribution to and persistence of VM202 in reproductive tissues was evaluated in rats. The ability of VM202 to induce humoral immune responses was evaluated following intramuscular administration with or without adjuvant in mice. All species utilized for these studies (mouse, rat, and rabbit) were shown in *in vivo* experiments to be able to express the plasmid following intramuscular injection.

An ischemic heart disease efficacy study in a Yorkshire swine model demonstrated that intramyocardial administration of VM202 increased the capillary density and regional perfusion in ischemic myocardium and improved ischemic left ventricular function. An ischemic heart disease efficacy study in rats demonstrated that

histologically identifiable capillaries increased following intramuscular administration of VM202 (versus pCK and pCK-VEGF₁₆₅; $p < 0.001$).

Collectively, VM202 has been well-tolerated in all studies conducted to date, with the only evidence of toxicity consisting of mild, transient injection site irritation in rats at a dose level 6-fold above the human clinical dose of 16 mg (0.23 mg/kg for a 70 kg patient), the maximum dose administered on a single day in the phase I study. There has been no evidence of systemic toxicity in any study and human HGF has not been detected in the sera of rats or rabbits following intramuscular injection [lower limit of quantitation (LLOQ) = 125 pg/mL]. There is no evidence of genomic integration, potential germ cell transmission, or immunostimulatory effects following intramuscular administration of VM202 to animals.

Therefore, the nonclinical efficacy and safety studies support the continued clinical investigation of VM202 in patients with critical limb ischemia.

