4.2.12. INJECTION SITE REACTION ASSESSMENT

Local injection sites reactions will be assessed on Day 0 post injection, pre and post injection on Days 14, 28 and 42, and on Day 49 using the grading defined by the National Cancer Institute's Common Terminology for Adverse Events v3.0. The grading categories are as follows and will be recorded on the CRF as described in Table 2.

Table 2. Injection Reaction Assessment

ADVERSE EVENT	GRADE 1	GRADE 2	GRADE 3	GRADE 4	GRADE 5
Injection site reaction	Pain, itching, erythema	Pain or swelling, with inflammation or phlebitis	Ulceration or necrosis that is severe; operative intervention indicated		
Ulceration		Superficial ulceration < 2 cm size; local wound care; medical intervention indicated	Ulceration ≥2 cm size; operative debridement, primary closure or other invasive intervention indicated (e.g.	Life-threatening consequences; major invasive intervention indicated (e.g., complete	Death

ADVERSE EVENT	GRADE 1	GRADE 2	GRADE 3	GRADE 4	GRADE 5
			hyperbaric oxygen)	resection , tissue reconstruction, flap, or grafting	
Allergic reaction / hypersensitivity	Transient flushing or rash; drug fever < 38°C (<100.4°F)	Rash; flushing ; urticaria; dyspnea; drug fever ≥38°C (≥100.4°F)	Symptomatic bronchospasm, with or without urticaria; parenteral medications(s) indicated; allergy-related edema/ angioedema; hypotension	Anaphylaxis	Death

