11.6. Injection Site Reaction

Assessments of the existence of an injection site reaction (Yes or No) are planned for Day 0 (post-dose), Day 14 (pre and post dose), Day 28 (pre and post dose), Day 42 (pre and post dose) and Day 49. The number and percentage of subjects with and without an injection site reaction will be summarized descriptively by treatment arm and study visit.

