^[1] Baseline defined as the last non-missing value prior to first dose of study drug.

^[2] Change = Change from Baseline

path\t_program.sas date time

Programmer Note Repeat for all available time points and vital signs.

Table 21
Retinal Fundoscopy- Shift from Baseline
Safety Population

	Screening/Baseline								
	Placebo (N=)		VM202- 8 mg (N=)		VM202- 16 mg (N=)				
	Normal	Abn, Not CS ^[1]	Abn, CS ^[2]	Normal	Abn, Not CS ^[1]	Abn, CS ^[2]	Normal	Abn, Not CS ^[1]	Abn, CS ^[2]
12 Months									
Right		n			n			n	
Normal	n (%)	n (%)	n (%)	n (%)	n (%)	n (%)	n (%)	n (%)	n (%)
Abnormal, Not Clinically Significant	n (%)	n (%)	n (%)	n (%)	n (%)	n (%)	n (%)	n (%)	n (%)
Abnormal, Clinically Significant	n (%)	n (%)	n (%)	n (%)	n (%)	n (%)	n (%)	n (%)	n (%)
Left		n			n			n	
Normal	n (%)	n (%)	n (%)	n (%)	n (%)	n (%)	n (%)	n (%)	n (%)
Abnormal, Not Clinically Significant	n (%)	n (%)	n (%)	n (%)	n (%)	n (%)	n (%)	n (%)	n (%)
Abnormal, Clinically Significant	n (%)	n (%)	n (%)	n (%)	n (%)	n (%)	n (%)	n (%)	n (%)

Note: In the case of an early withdrawal, the result from the last retinal fundoscopy is considered for the 12 Months visit.

[¹] Abn, Not CS= Abnormal, Not Clinically Significant

[²] Abn, CS= Abnormal, Clinically Significant

path\t_program.sas date time

Table 22
Injection Site Reaction
Safety Population

	Placebo (N=)	VM202- 8 mg (N=)	VM202- 16 mg (N=)
Subject reported an Injection Site Reaction?			
Day 0 (Post-Dose)			
Yes	n n (%)	n n (%)	n n (%)
No	n n (%)	n n (%)	n n (%)
Day14 (Pre-Dose)			
Yes	n n (%)	n n (%)	n n (%)
No	n n (%)	n n (%)	n n (%)
Day14 (Post-Dose)			
Yes	n n (%)	n n (%)	n n (%)
No	n n (%)	n n (%)	n n (%)
Etc.			

path\t_program.sas date time

Programmer Note Repeat for all available time point, Day 28(pre- and post-dose), Day 42(pre- and post-dose), and Day 49(pre- and post-dose).

[figure not shown]
Table 23
Prior and Concomitant Medications
Safety Population

ATC Drug Class / Medication Term	Placebo (N=)	VM202- 8 mg (N=)	VM202- 16 mg (N=)
Subjects Receiving any Concomitant Medications	n (%)	n (%)	n (%)
Drug Class 1	n (%)	n (%)	n (%)
Medication Term 1	n (%)	n (%)	n (%)
Medication Term 2	n (%)	n (%)	n (%)
.	.	.	.
Drug Class 2	n (%)	n (%)	n (%)
Medication Term 1	n (%)	n (%)	n (%)
Medication Term 2	n (%)	n (%)	n (%)
.	.	.	.
Etc.			

Note: At each level of summation (overall, ATC drug class, medication term), subjects reporting more than medication are counted only once.
path\t_program.sas date time

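### Table 22 cannot show the grade of injection-site reactions, and its pre-dose rows count persistence, not new delayed reactions after the first three injection sessions

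*SAP*

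**What the plan says.** Protocol 4.2.12 schedules local reaction checks at "Day 0 post injection, pre and post injection on Days 14, 28 and 42, and on Day 49 using the grading defined by" the NCI common terminology, version 3.0. On recording it says: "The grading categories are as follows and will be recorded on the CRF as described in Table 2". That table separates, for example, Grade 1 pain, itching or redness from Grade 3 severe ulceration or necrosis.

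SAP 11.6 plans a binary variable. It begins "Assessments of the existence of an injection site reaction (Yes or No) are planned for Day 0 (post-dose") and goes on to list the pre- and post-dose checks on Days 14, 28 and 42, and Day 49. The analysis is: "The number and percentage of subjects with and without an injection site reaction will be summarized descriptively by treatment arm and study visit".

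In SAP Appendix B, Table 22 has Yes and No rows at each time point, under a row heading that asks whether the subject reported an injection-site reaction. Its programmer note asks for "Day 49(pre- and post-dose") results.

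In SAP Appendix D, Listing 37 shows Yes/No and, for a Yes, an AE number. Its footnote reads "For Pre Injection time Points, response shown is to the question" that follows, namely "If an injection site reaction occurred at the previous visit, is it still present".

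**The concern.** Two things are lost between the protocol and the dedicated safety table.

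First, the grade. The protocol has it recorded, but the table counts transient itching and severe ulceration alike.

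Second, the meaning of the pre-dose rows. They look like incidence by visit. By the listing footnote they hold the answer to a persistence question, which presupposes a reaction at the previous visit. A reaction that starts some days after a clean same-day check has no natural Yes there.

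Safety is the primary objective (SAP 2.1). Each patient receives 4 × 16 = 64 injections into one calf, of which 64, 32 or 0 are VM202 in the high-dose, low-dose and placebo arms. Protocol 1.6 describes "the only evidence of toxicity consisting of mild, transient injection site irritation in rats", so local tolerability is the natural place to look for a signal. The low-dose arm also changes from VM202 to saline on Days 28 and 42. Assigning a between-visit reaction to the session before it would therefore be informative, and Table 22 does not do this.

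**Working it through.** The plan states no figure on this point, so there is none to reproduce. The check sets the passages side by side and then gives an illustration of size. A session here means one visit with 16 injections.

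**Step 1: what each assessment point carries.** There are 4 post-dose + 3 pre-dose + 1 (Day 49) = 8 points.

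| Points | Protocol 4.2.12 | Table 22 and Listing 37 |
|---|---|---|
| Post-dose, Days 0, 14, 28, 42 (4) | assessed and graded | Yes/No |
| Pre-dose, Days 14, 28, 42 (3) | assessed and graded | Yes/No to persistence from the previous visit |
| Day 49 (1) | assessed and graded | Yes/No; the persistence footnote names pre-injection points only |

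**Step 2: a delayed reaction followed through the table.** Take a patient with a clean check after the Day 0 injections and local inflammation starting on day 3.
- The Day 14 pre-dose item asks about a reaction at the previous visit. There was none, so a literal answer is not Yes.
- The same holds from Day 14 to Day 28 and from Day 28 to Day 42.
- After session 4 the next check is Day 49. No injection is given then (Protocol 3.4.10), so it is not a pre-injection point and a delayed reaction may be a Yes.
- The gap therefore covers sessions 1 to 3.
- If the reaction is still present at the Day 14 post-dose check, it may be a Yes there, but it then sits with session 2 and not with session 1.
- A pre-dose No can mean never present, resolved, or newly arisen. The percentage has no single reading.

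**Step 3: grade.** Table 22 has no grade row and Listing 37 has no grade column. No other planned table or listing shows the CTCAE injection-site grade.

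**Step 4: the AE route.** Protocol 5.2 requires all AEs after first dosing to be recorded with onset date, severity, and relationship to study medication, injection procedure and underlying disease. Tables 14 to 17 and Listing 28 would carry a delayed reaction reported in this way. Three limits apply:
- The intensity scale in Protocol 5.2.2 is mild, moderate or severe, judged by how far the event limits daily activity. It is not the local CTCAE scale.
- Table 16 tabulates relationship to study drug only. Relationship to procedure appears only in the AE and SAE listings, although Protocol 6.2.3 plans to describe AEs by procedure as well.
- Listing 37 gives an AE number only for a Yes, so a delayed reaction that is never a Yes has no link.

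**Step 5: illustration of size.** The inputs are 50 patients (Protocol 3.3), three affected sessions (Step 2), and an assumed delayed-reaction rate p per session of 10% (range 5–20%). The rate is not from the documents. All patients are taken to receive the first three sessions, and sessions are taken as independent.
- Sessions: 50 × 3 = 150.
- Affected sessions, 150 × p: 7.5, 15 and 30 for p = 0.05, 0.10 and 0.20.
- Patients with at least one, 1 − (1 − p)³: 1 − 0.95³ = 14%; 1 − 0.90³ = 27%; 1 − 0.80³ = 49%.
- VM202 sessions among the 150: 20 × 2 (low dose) + 20 × 3 (high dose) = 100. At the same rates, 5, 10 and 20 affected sessions would follow VM202 and the rest saline.

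**The case against.** The strongest reply is that the plan already captures these events. An adverse event assessment is scheduled before injection on Days 14, 28 and 42 (Protocol 3.4.7.1, 3.4.8.1, 3.4.9.1) and on Day 49 (3.4.10). A day-3 ulceration belongs in the AE record, with its onset date, and in the tables by term, maximum severity, relationship and seriousness. This stands, and it confines the point to Table 22 and Listing 37.

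It also rules out three stronger readings that a reader might infer:
- *Delayed VM202 reactions would be missed by the trial and their severity hidden.* The documents do not support this. Reactions reported as AEs remain visible, on a different scale.
- *Severe reactions do not appear in Table 22.* They do appear as a Yes if present at a post-dose check, if persisting from one, or if seen on Day 49. What is lost is the grade.
- *All four sessions are affected.* Day 49 is not a pre-injection point, so only sessions 1 to 3 are.

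Two further cautions are fair. The CRF is not among the documents. The item wording is inferred from the listing footnote, and the CRF page may hold a grade field or a prompt for new reactions. And the preclinical irritation was mild and transient, in rats, at 6-fold above the human clinical dose. It gives a reason to look at local tolerability but does not indicate expected harm.

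The Day 49 pre/post label is a slip in a programmer note, since SAP 11.6 lists Day 49 without a split. Its only consequence is to blur which question applies that day.

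**Conclusion.** The point holds for the dedicated output. Table 22 cannot show reaction grade, although the protocol requires it to be recorded. Its pre-dose rows on Days 14, 28 and 42 (3 of the 8 assessment points) report persistence under a label that reads as reactions reported. New delayed-onset reactions after sessions 1 to 3 are not counted in those rows and must be sought in the AE outputs.

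The size cannot be known from the documents. Under the assumed 10% rate and independence it is 15 of 150 sessions (7.5–30) and 27% of patients (14–49%). These figures show scale and are not a forecast. The textual finding does not depend on them. It rests on reading the Listing 37 footnote as the wording of the CRF item.

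This is a mislabelled and incomplete safety summary in a trial whose primary objective is safety. It should be corrected, but it does not undermine the AE analysis.

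**What to change.** In SAP 11.6 and Table 22, report by arm the number of subjects with any injection-site reaction by worst CTCAE grade, overall and per session. Assign a reaction that arises between visits to the preceding session. Add the grade to Listing 37.

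If the CRF can still change, ask at each pre-dose check and on Day 49 for any new or continuing reaction since the last assessment, with onset date and grade.

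If the CRF cannot change, identify between-visit reactions from AE terms, onset dates and relationship to procedure. Linked AE numbers alone are not enough, because they exist only for a Yes. Relabel the pre-dose rows of Table 22 as persistence of a reaction from the previous visit.

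Remove the Day 49 pre/post split from the programmer note.

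The cost is one table, one listing column and, where possible, one CRF item. No new assessments are needed, since the protocol already requires the checks and the grades. Reported reaction rates may rise, and there is slightly more analysis work.
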